While PRP shows promise in helping restore function to these patients, there are still concerns with PRP's long term outcomes. Another option that has become more popular for physicians treating this debilitation condition is bone marrow aspirate concentrate (BMA), which uses undifferentiated cells found in the bone marrow to promote healing and tissue

regeneration.¹³ These cells have the ability to replicate into a multiple different tissue types. With BMA, the marrow is concentrated provide better healing of the damaged tissue and aid in growth and repair. The full benefits of BMA are still unknown, but studies have shown the treatment can reduce swelling, relieve pain, and improve healing in articular cartilage and bone grafts.¹⁴

Autologous BMA has shown promising clinical potential as a therapeutic agent in regenerative medicine, including the treatment of osteoarthritis and cartilage defects,¹³⁻¹⁴ and the clinical efficacy platelet rich plasma has been documented to alleviate symptoms related to knee osteoarthritis.²⁻⁸ However, randomized, prospective comparison of the two techniques has not been reported in the literature and long term follow-up for both treatments is limited, and especially limited in the use of BMA for osteoarthritis treatment.

2 Objectives

The main objective of this study is to compare the effectiveness of bone marrow aspirate concentrate (BMC) to platelet rich plasma (PRP) injections for the treatment of knee osteoarthritis in regards to pain and function at multiple time points up to 24 months post injection.

3 Subject Eligibility

Patients between the ages of 18 and 80, with evidence of knee osteoarthritis will be screened for eligibility in the study. All subjects must present with pain or swelling of the knee of at least 4 months in duration and a Kellgren-Lawrence score between 1

and 3 upon x-ray evaluation. Potential subjects must be willing and able to provide informed consent and be willing and able to return for scheduled follow-up visits.

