Exclusion criteria include: Patients with major mechanical axis deviation of more than 50% into either compartment (varus or valgus) or that have had a corticosteroid injection within 3 months or a hyaluronic acid injection within 6 months will not be eligible. Patients will be excluded if they have a history of the following medical conditions - diabetes, autoimmune disorders, disorders requiring immunosuppression, rheumatoid arthritis, hemophilic arthropathy, infectious arthritis, Charcot's knee, Paget's disease of the femur or tibia, or history of cancer. In addition anyone with an ongoing infectious disease or significant cardiovascular, renal or hepatic disease will be excluded.

4 Subject Enrollment

120 patients will be recruited through physician practices and with print, flyer or web based advertisements (AREF and EmCYTE websites). Those patients who contact the clinical trials department through the physician's office or by referral from an advertisement or otherwise will be prescreened for adherence to the inclusion and exclusion criteria via phone or in person.

Once the potential participant has been prescreened for inclusion and exclusion criteria, and agreed to be screened for participation in the study they will be instructed on study enrollment protocols which will include a visit with one of the physician investigators for evaluation, x-ray's and confirmation of adherence to the inclusion criteria. Subjects will also be instructed that they must not take any prescription or over the counter non-steroidal anti-inflammatory drugs (NSAIDS) for 3 weeks prior to the evaluation appointment. Following the physician evaluation and confirmation subjects will again have all study requirements explained to them and go through the described informed consent process. The subject will then be randomly placed in one of the two study groups and be scheduled to receive either a PRP injection or BMC injection in their affected knee.

5 Study Design and Procedures

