Upon enrollment and completion of the informed consent process, patients will be randomized into the 2 study groups of 60 each, based on a list compiled by a random number generator prior to initiation of the study. Both Groups will complete the Western Ontario and McMaster Universities Osteoarthritis Index (WOMAC), and the Subjective International Knee Documentation Committee Subjective Score (IKDC) questionnaires prior to any treatment. Due to the invasive nature of obtaining marrow aspirate blinding of the subjects and clinicians will not be performed. Group 1 [PRP]: Will receive a single (1) intra-articular injection of PRP. Group 2 [BMC]: Will receive a single (1) intra-articular injection of BMC after obtaining informed consent. Both types of injections and all associated procedures will be performed in the clinic or lab setting with local anesthesia. Following the injection patients will be asked to complete a short questionnaire documenting the BMC or PRP collection, preparation and injection experience. Ten patients will be randomly selected from both (20 total subjects) the PRP and

BMC groups to have analysis performed on the BMC and PRP as described below. This analysis will not be performed on patients not randomly selected. In patients randomly selected after the BMC or PRP have been prepared for injection, a small sample (1 mL) of the BMC or PRP will be separated and sent to an independent lab (Biosciences Research Associates, Inc) for analysis. The PRP will be analyzed with a CBC and the BMC will be analyzed for TNC, human CD34+ hematopoietic stem/progenitor cell assay, CFU-F, plasma free hemoglobin, cell viability percent, and hemolysis percent. Evaluation, a 4 view x-ray series (long leg, lateral, sunrise, and bilateral Rosenberg), and injections will be provided at no charge to the patients. Patients will then be given standard follow-up care instructions that include no use of NSAIDS for at least 7 days and partial weight bearing on the limb for 2-3 days, followed by the initiation of a standard physical therapy program at one week following injection.

After the injection subjects will be required to complete the WOMAC and IKDC questionnaires as well as report any medications they are using via email or phone (paper method will be available on request) at 1, 3, 6, 9, 12, 18, and 24 months following the injection.

PRP protocols

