All personal information is strictly confidential and no names will be disclosed except as required by law. All research information will be managed and accessible by only the named investigators and their medical staff. Data sheets will have names and identifying information replaced with a subject code to protect the confidentiality of the subject. All information provided by the subject during this project will be recorded on the appropriate forms and stored in a locked room in the AREF research facility. In addition all subject data forms will be scanned and stored, along with summary information forms, spreadsheets, and photos, in a secure password protected folder on a laptop in which only study investigators will have access to, and will be permanently deleted following any and all publications or presentations have been completed related to this research. All records related to this research will be retained in a secure location for a period of 3 years following the completion of all study related activities, at which time they will be properly destroyed.

8 Data Analysis

All data will be entered into an excel spreadsheet for analysis that will include obtaining standard measures such as means and standard deviation. Data will be analyzed as scores on the two questionnaires as well as across subsets of the individual questionnaires for function, quality of life and pain scores. Additional determinations based on medication usage and failure rates will be examined as well.

9 Statistical Considerations

A power analysis was performed to determine sample size based upon recent clinical trials comparing PRP to HA for the treatment of osteoarthritis. Analysis utilized the average of standard deviation to detect average of group mean effect at 80% power. This determined that 25 patients per group would be needed to reach statistical significance with the WOMAC and that 50 patients would be needed per group for the IKDC. Considering a potential dropout rate of 20%, 60 patients per group was chosen as the sample size.

Data will be analyzed for differences between groups using a repeated measures ANOVA design, using a significant p-value of < 0.05 for rejecting the null hypothesis. Additional subjective analysis will be performed on data involving the patient experience with regards to the injection.

10 Quality Control and Assurance

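### Kellgren-Lawrence grade is read for every patient before randomisation but used only for eligibility; prespecifying it as a covariate would recover a little precision at almost no cost.

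*Combined protocol and SAP*

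**What the plan says.** Section 3 (Subject Eligibility) requires of all subjects "a Kellgren-Lawrence score between 1" and 3 on x-ray. Section 4 (Subject Enrollment) sets the order of steps. Screening includes "a visit with one of the physician investigators for evaluation, x-ray's and confirmation of adherence to the inclusion criteria"; consent follows, and after that "The subject will then be randomly placed in one of the two study groups". The grade is therefore known for everyone before allocation.

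Section 5 (Study Design and Procedures) assigns 120 patients equally to the two arms. The assignment is "based on a list compiled by a random number generator prior to initiation of the study". The section names no stratum, block or minimisation factor.

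Section 9 (Statistical Considerations) gives the model: "Data will be analyzed for differences between groups using a repeated measures ANOVA design". It names no covariate. Section 8 (Data Analysis) adds summaries "across subsets of the individual questionnaires for function, quality of life and pain scores", plus medication use and failure rates. The subsets in that sentence are groups of questionnaire items, not groups of patients. Kellgren-Lawrence grade appears as an entry criterion and nowhere else.

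**The concern.** Eligibility spans three radiographic grades, and grade may be related to the WOMAC and IKDC scores. A single list that ignores grade lets the arms differ on it by chance, and a model without a grade term leaves any variance that grade explains in the error. Two things are at stake. One is a small loss of precision in a plan with no slack for the IKDC. The other is that, if the arms turn out unequal on grade, a decision to adjust made after seeing the results would look selective. Grade is already collected for everyone before allocation, so using it needs no new data.

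**Working it through.** **The plan's own figures.** Section 9 gives 25 per group for the WOMAC, 50 for the IKDC, 20% dropout and a final 60 per group. 50 × 1.20 = 60 reproduces the final figure. The 25 and 50 cannot be reproduced, because no mean difference or SD is given. Solving backwards at 80% power and two-sided 0.05 (sidedness is assumed), d = (1.960 + 0.842) × √(2/n), which gives 0.79 SD for n = 25 and 0.56 SD for n = 50. With 20% dropout, 60 × 0.80 = 48 completers per arm.

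**Assumptions, not in the documents.**
- Grade 3 makes up 30-50% of the 120 patients, that is K = 36 to 60.
- Grade 3 differs from grades 1-2 by e = 0.3-0.5 SD on the outcome. The true value could be zero.

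**Chance imbalance.** With 120 patients split 60/60, the number of grade 3 patients in one arm is hypergeometric (120, K, 60). The difference between arms is even when K is even and odd when K is odd, so every K from 36 to 60 has to be covered.

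| Gap in grade 3 count | Even K | Odd K | All K |
|---|---|---|---|
| At least 6 (6/60 = 10 points) | 0.319-0.361 | 0.235-0.273 | about 24-36% |
| At least 9 (9/60 = 15 points) | 0.072-0.100 | 0.113-0.144 | about 7-14% |

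For even K a gap of exactly 9 cannot occur, so those entries are for 10 or more.

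**Effect of a gap on the estimate.** Shift = gap × e.
- 10 points: 0.10 × 0.3 = 0.03 SD to 0.10 × 0.5 = 0.05 SD.
- 15 points at the largest assumed effect: 0.15 × 0.5 = 0.075 SD.

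With 48 per arm the standard error of the difference is √(2/48) = 0.204 SD, so significance needs 1.96 × 0.204 = 0.40 SD. Given a 10-point gap, type I error is 5.2-5.7% instead of 5%; given a 15-point gap at e = 0.5, it is about 6.6%.

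Averaged over possible lists, the shift has SD e × √(4p(1−p)/119), where p is the grade 3 share. This runs from 0.3 × 0.084 = 0.025 to 0.5 × 0.092 = 0.046 SD.

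**Precision recovered.** The share of variance explained by grade is R² = p(1−p)e². It runs from 0.30 × 0.70 × 0.09 = 0.019 to 0.50 × 0.50 × 0.25 = 0.0625. Adjustment multiplies the SD by √(1−R²). At d = 0.56 and 48 per arm:

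| R² | Power |
|---|---|
| 0 (no adjustment, or no effect of grade) | 78.4% |
| 0.019 | 79.1% |
| 0.04 | 80.0% |
| 0.0625 | 80.9% |

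At R² = 0.04, 48/(1 − 0.04) = 50, so 48 adjusted patients per arm have the precision of 50 unadjusted. These R² values take no account of the baseline score. Whatever severity the baseline WOMAC or IKDC already carries would reduce the gain.

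**The case against.** The strongest reply is that nothing here is wrong. Simple 1:1 randomisation is valid, and leaving out a prognostic covariate does not invalidate the test, because chance imbalance is already part of the standard error. That stands in full.

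A reader might infer that, in an open-label trial, imbalance on grade would be a ready explanation for any modest difference. The documents do not support this. They give no relation between grade and outcome, and even under the assumptions above a 15-point gap moves the estimate by 0.075 SD, under one fifth of the 0.40 SD needed for significance.

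It is also fair to say that the documents rank no prognostic factor, so preferring grade to age or alignment is a matter of judgement. Further, both questionnaires are completed before treatment (section 5). If those scores enter the model, grade helps only where it predicts outcome beyond them. How baseline enters is not stated, and that is the larger gap. Both remarks stand and limit the weight of the point.

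Finally, stratifying the list has a cost. Section 5 states that neither subjects nor clinicians are blinded, and small blocks within strata make the next allocation somewhat more predictable. What survives is the narrower point that a baseline measurement held for every patient goes unused in the analysis.

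**Conclusion.** The omission is confirmed: grade is known before allocation, no stratification is described, and no analysis uses grade. That the list is unstratified is inferred from a single list and silence on strata; the protocol does not say so in words. The consequence is small. A 10-point gap is fairly likely (about 24-36%) but shifts the difference by only 0.03-0.05 SD, and adjustment takes IKDC power from 78.4% to about 79-81% at most. All of this assumes 30-50% grade 3, an effect of 0.3-0.5 SD, two-sided testing and the back-solved 0.56 SD. If grade has no effect, or the baseline score already captures it, the gain is nil or close to it. This is a minor, near-free improvement. The documents do not support reading it as a biased comparison or as a flaw that would undermine the result.

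**What to change.** In section 9, prespecify Kellgren-Lawrence grade (1-2 versus 3) and the baseline score of the questionnaire concerned as fixed covariates in the WOMAC and IKDC models. Do this before any outcome data by arm are seen. Grade costs one degree of freedom and needs no new data, visit or x-ray.

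Stratifying the list by grade is optional and makes sense only if enrolment has not begun, which the documents do not show. It would mean two lists to administer. Block sizes should be concealed and randomly varied, with the added predictability in an open-label trial weighed against a small gain. If enrolment has started, the model term alone is enough. If strata were in fact intended, stating them in section 5 settles the allocation part of the point.

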All protocols will be monitored and analyzed data will be checked for accuracy by the principal investigator and/or a designated AREF research team member. All medical data will be kept in compliance with HIPAA guidelines.

11 Regulatory Requirements

Informed Consent:

The informed consent process will be performed by a study coordinator from the Andrews Research and Education Foundation. All subjects will have the study described to them and will be given as much time as they would like to read an approved, stamped version of the informed consent document. After signing the informed consent document, they will be given a copy for their records.

Subject Confidentiality:

Subject confidentiality information is listed above in #7 (Data Management Procedures). All medical data will be recorded and stored in compliance with HIPAA guidelines.

12 References

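### No concealment step is described for the pre-compiled allocation list in this open-label trial, and baseline scores may be taken after the arm is known

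*Combined protocol and SAP*

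**What the plan says.** **Sequence.** Section 5 (Study Design and Procedures) allocates 120 patients equally to the two arms, and the allocation is "based on a list compiled by a random number generator prior to initiation of the study". This describes how the sequence is made. No block size or stratification is given.

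**Blinding.** The same section states: "Due to the invasive nature of obtaining marrow aspirate blinding of the subjects and clinicians will not be performed". The outcomes, WOMAC and IKDC, are questionnaires that the patients complete.

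**Eligibility and consent.** Section 4 (Subject Enrollment) requires "a visit with one of the physician investigators for evaluation, x-ray's and confirmation of adherence to the inclusion criteria". Consent follows. Section 11 adds: "The informed consent process will be performed by a study coordinator from the Andrews Research and Education Foundation".

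**Assignment.** After consent, Section 4 continues: "The subject will then be randomly placed in one of the two study groups". The injection is then scheduled.

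**Baseline scores.** Section 5 mentions the baseline questionnaires after the randomisation sentence. It requires both groups to complete them before treatment, but not before assignment.

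**Access.** Section 7 (Data Management Procedures) states: "All research information will be managed and accessible by only the named investigators and their medical staff". The allocation list is not excepted.

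**The concern.** Randomisation protects against selection bias only if nobody who decides on a patient's entry knows which arm comes next. A list made in advance and kept where recruiting staff can read it gives that knowledge for every patient. A physician or coordinator who prefers one treatment for certain patients could then judge eligibility, time the visit or present the study differently according to the next entry.

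Concealment matters more here than in a blinded trial. Patients and clinicians know the treatment and patients score their own outcomes, so nothing later in the conduct of the trial would offset a difference in who was enrolled. An imbalance in unmeasured prognosis also cannot be removed in the analysis.

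The timing of baseline scores is a second route to bias. A patient who already knows whether marrow aspiration is coming may score pain and function differently. If results are read as change from baseline, an arm-related shift of a given size in baseline scores moves the between-arm difference in change by the same amount.

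**Working it through.** **1. What is described.** No figure in the plan decides this point, so the first check is of the text.

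| Element | Described? |
|---|---|
| How the sequence is generated | Yes, Section 5 |
| Who holds the list | No |
| Who makes the assignment | No |
| How the next entry is hidden (central system, envelopes) | No |
| Eligibility and consent before assignment | Yes, Sections 4 and 5 |
| Baseline WOMAC/IKDC before assignment | No, only before treatment |
| List exempt from investigator access | No, Section 7 |

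The appendices cited (technique manual, safety data sheets, centrifuge manual, FDA letters, specimen kit) are not described as covering allocation.

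**2. How predictable the next assignment is.** There are 120 patients, 60 per arm.

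- *Readable list:* 120 of 120 known (100%).
- *Hidden, unblocked 60/60 list:* someone who remembers past open-label assignments and always guesses the arm that is behind expects 60 + [2^119 / C(120,60) − 1/2] = 60 + 6.4 = 66.4 correct, or 66.4/120 = 55.3%, against 50% by chance. The expected number of final entries that become certain because one arm is full is 2 × 60/(60 + 1) = 120/61, about 2.
- *Hidden list in fixed blocks of known size b:* the excess over 60 is (120/b) × [2^(b−1) / C(b, b/2) − 1/2]. For b = 4 this is 30 × (8/6 − 1/2) = 25, so 85/120 = 70.8%. Blocks of 2, 6 and 8 give 75.0%, 68.3% and 66.6%.
- *Hidden list in randomly varied blocks of unknown size:* by simulation, the same guessing rule is right about 70% of the time for sizes 2/4/6, 69% for 4/6 and 68% for 4/6/8.

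A readable list is therefore the main exposure. Small blocks would make a hidden list easier to guess than an unblocked one.

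**3. What a prognostic gap would do.** Sections 5 and 9 give 60 per group and 20% dropout, so 60 × 0.80 = 48 per arm. Section 9 gives a 0.05 significance level; two-sided is assumed. The gap g, in SD units, is an assumption. For a two-sample t-test with no true treatment effect, the noncentrality is g × √(48/2) with 94 degrees of freedom.

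| Assumed gap g | Noncentrality | Chance of p < 0.05 |
|---|---|---|
| 0.1 SD | 0.49 | 7.7% |
| 0.2 SD | 0.98 | 16.3% |
| 0.3 SD | 1.47 | 30.7% |

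With all 60 per arm, a normal approximation gives 8.5%, 19.5% and 37.6%.

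**The case against.** **The plan is silent; it does not say the list is open.** This stands. A reader might infer from Section 7 that physicians can look up the next entry, but no text says that they do or that the list is kept with the study records. The supportable statement is that no concealment is described and that the access rule, read literally, does not prevent foreknowledge.

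**Eligibility and consent already precede assignment.** This stands as a partial safeguard. It fails only if the next entry is known at those steps, and nothing in the plan ensures that it is not. The order does not cover the baseline questionnaires.

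**There is little room or motive to steer.** Most entry criteria are fixed items: age, Kellgren-Lawrence grade, injection windows and listed diagnoses. The main discretionary one is significant cardiovascular, renal or hepatic disease, which has no threshold. Both kits come from the company that funds the trial, so the documents show no obvious commercial reason to favour one arm. This lowers the likely size of any bias, but deferral and persuasion need no discretionary criterion.

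**Open treatment and a fixed 60/60 total do not by themselves reveal the sequence.** A reader might infer that they do. With a hidden unblocked list, guessing is 55.3% correct and about 2 of 120 entries become certain, so this is a minor point.

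**The error rates are not estimates for this trial.** This also stands. The gap is assumed, steering would have to run consistently in one direction to produce it, and the plan specifies repeated measures ANOVA, not a single t-test.

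**Conclusion.** The concern holds as a gap in the procedure. The plan describes a list made in advance, unblinded physicians who confirm eligibility, and an access rule that does not exempt the list. It describes no means of hiding the next entry. Followed as written, it permits foreknowledge of the arm and permits baseline patient-reported scores to be given with the arm known.

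The documents do not support a stronger reading, that allocation was open or that patients were steered. They also give no basis for the size of any bias. The rise from 5% to about 8%, 16% or 31% is conditional on assumed gaps of 0.1, 0.2 or 0.3 SD, two-sided testing and 48 completers per arm. The point should still be settled before enrolment, because it concerns conduct, costs little to close and cannot be repaired in the analysis.

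**What to change.** Amend Sections 4, 5 and 7 as follows.

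1. Keep one shuffled list of 60 and 60. Do not use small permuted blocks, which would raise predictability in an open trial. The price is less control of balance over time, so the arms could be unequal if recruitment stopped early.
2. Name, by role, a holder of the list who does not screen, obtain consent or treat.
3. Exempt the list from the access rule in Section 7.
4. Release one assignment at a time, by a locked electronic module or sequentially numbered opaque sealed envelopes.
5. Release it only after eligibility sign-off, consent and baseline WOMAC and IKDC are recorded, and date each step.

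The cost is protocol wording and minor administration, with no extra patients. It assumes that a suitable holder is available. The protocol mentions a study coordinator, who takes consent and so could not serve, and an unspecified member of the foundation's research team. If enrolment has already begun, the report should say who held the list and, for each patient, whether baseline scores came before or after assignment.

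### Open-label randomisation precedes a scheduled injection and all follow-up is timed from that injection, so a randomised patient who is not injected has no planned outcome

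*Combined protocol and SAP*

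**What the plan says.** The order of events comes from two places in the combined protocol and SAP. Section 4 (Subject Enrollment) puts physician evaluation, confirmation of eligibility and consent first, and continues: "The subject will then be randomly placed in one of the two study groups and be scheduled to receive either a PRP injection or BMC". Section 5 (Study Design and Procedures) agrees: "Upon enrollment and completion of the informed consent process, patients will be randomized into the 2 study groups of 60 each". Neither section states an interval between randomisation and injection.

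On knowledge of the arm, Section 5 says: "Due to the invasive nature of obtaining marrow aspirate blinding of the subjects and clinicians will not be performed".

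On outcomes, Section 5 asks both groups for baseline WOMAC and IKDC "questionnaires prior to any treatment", with no requirement that this comes before randomisation. For everything later it says: "After the injection subjects will be required to complete the WOMAC and IKDC questionnaires". The seven time points, from 1 to 24 months, are counted from the injection, and the medication reports follow the same schedule. Section 2 (Objectives) also counts time from the injection.

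Sections 8 and 9 name a repeated measures ANOVA and a 20% dropout allowance. They define no analysis population and no handling of missing data, and they do not mention patients who are randomised but never injected.

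**The concern.** Collection of outcomes is triggered by receiving the treatment, and the arm can be known before that trigger. A patient who learns the allocation and then does not go ahead falls outside the follow-up schedule as written. If such patients differ in prognosis from those who go ahead, and the two arms lose different numbers or kinds of patients, the analysed groups are no longer the randomised groups. An analysis-stage method has little to work with when no post-baseline score was collected.

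A second consequence concerns baseline. WOMAC and IKDC are self-reported. If they may be completed after the patient knows the arm, expectation or disappointment can enter the baseline scores, and through them any comparison that uses baseline.

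**Working it through.** **1. The passages side by side.**

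| Step | Where | What is fixed | What is open |
|---|---|---|---|
| Consent | Sections 4, 5, 11 | Before randomisation, all patients | – |
| Randomisation | Sections 4, 5 | After consent | Interval to injection |
| Knowledge of arm | Section 5 | Open label | When the patient is told |
| Baseline scores | Section 5 | Before treatment | Before or after randomisation |
| Follow-up scores | Sections 2, 5 | Counted from injection | Patients not injected |
| Analysis set | Sections 8, 9 | – | Not defined |

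The PRP and BMA procedure texts in Section 5 say that the process is completed in one visit. They describe collection, preparation and injection. They do not place randomisation at that visit, so they do not close the gap.

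**2. The plan's own sample size.** Section 9 needs 50 per group for IKDC and allows 20% dropout. 50 × 1.20 = 60 reproduces the stated figure; 50 / (1 − 0.20) = 62.5, or 63, does not. With 60 randomised and 20% lost, 60 × 0.80 = 48 remain, below the plan's own 50. The inflation method is a separate matter. Here it shows only that there is no reserve for extra loss.

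**3. A reference effect.** Section 9 gives no effect size or SD. Assuming a two-sided 5% test (sidedness is not stated) and 80% power with 50 per group, the normal approximation gives d = √(2/50) × (1.960 + 0.842) = 0.2 × 2.802 = 0.56 SD.

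**4. Illustrative shift in an arm mean.** Assume x of 60 patients in one arm are lost before injection, none in the other arm, and that those lost differ by s SD from the full-arm mean. Then shift = (x/60) × s / (1 − x/60) = x × s / (60 − x).

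| x | s = 0.5 | s = 1.0 |
|---|---|---|
| 3 | 3 × 0.5 / 57 = 0.026 | 3 / 57 = 0.053 |
| 6 | 6 × 0.5 / 54 = 0.056 | 6 / 54 = 0.111 |
| 9 | 9 × 0.5 / 51 = 0.088 | 9 / 51 = 0.176 |

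Against 0.56 SD, the range 0.026 to 0.176 is about 5% to 31%. If the gap is instead measured between those lost and those who stay, the shift is (x/60) × gap, which gives 0.025 (3 lost, 0.5 SD) to 0.15 (9 lost, 1.0 SD).

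**5. Power.** Power = Φ(0.56 / √(1/n₁ + 1/n₂) − 1.96), using the unrounded d. With 48 v 48 it is 78.4%. If 3, 6 or 9 patients are lost from one arm before a further 20% dropout, the numbers are 48 v 45.6 (77.3%), 48 v 43.2 (76.2%) and 48 v 40.8 (74.9%). If the 20% already includes these losses, power stays at 78.4%. The power cost is modest, so selection is the main issue.

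**The case against.** The strongest reply is that consent precedes randomisation, after all study requirements have been explained, so every patient has already agreed to either procedure. Refusals should be few. That stands as a reason to expect small numbers. It does not remove the gap, because the patient consents before knowing the arm and the plan makes no provision for those who then stop.

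A reader might infer that the loss must fall mainly on the BMC arm. The harvest is described as invasive, and Section 6 lists harvest-site and heparin risks that belong only to it, so this is plausible. The documents give no rate, however, and Sections 1 and 2 offer a contrary pull: they raise doubts about long-term results with PRP and describe marrow concentrate as promising. Patients hoping for BMC could leave the PRP arm.

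A reader might also infer a second chance to opt out in Group 2, from "Will receive a single (1) intra-articular injection of BMC after obtaining informed consent". Sections 4, 5 and 11 describe one consent process before randomisation, so this is probably loose drafting.

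Two further inferences go too far. Being scheduled does not establish a long or variable wait, so symptom drift differing between arms has no support in the text. And it is not established that uninjected patients have no score at all, since a baseline may exist.

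Finally, the 20% allowance may already include pre-injection loss: 20% of 60 is 12 patients. That weakens the power argument but not the selection argument. Also, if baseline is one of the repeated measures, a stable difference in severity would largely cancel from the group-by-time comparison. The gap that matters would then be in expected change.

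**Conclusion.** The point holds as a structural gap. Followed as written, the plan schedules no post-baseline outcome for a randomised patient who is not injected, and it permits baseline self-reports after the arm is known. No section rebuts either statement.

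Its size and direction cannot be determined from the documents. The shift of 0.03 to 0.18 SD rests on three assumptions: loss of 3 to 9 of 60, confined to one arm, with a difference of 0.5 to 1.0 SD from the full-arm mean. It shows what such a loss would do and is not an estimate of what will happen. At the low end it is negligible; at the high end it is nearly a third of the implied detectable difference. A definite bias against or in favour of BMC, a separate consent step for Group 2, and arm-specific symptom drift are not supported. The change should be made because it is cheap and because outcomes never collected cannot be recovered later.

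**What to change.** - Require baseline WOMAC and IKDC to be complete before randomisation.
- Open the allocation as close to the procedure as practicable, preferably at the injection visit. If same-day randomisation is already intended, say so.
- Send the 1 to 24 month questionnaires by the existing email or phone route to every randomised patient who has not withdrawn consent, injected or not.
- Use randomisation as the one time origin for all patients and align Section 2 with it. With allocation at the injection visit, the two origins nearly coincide for injected patients.
- State in Section 9 that patients are analysed as randomised, and report pre-injection withdrawals by arm.
- Clarify that the consent wording for Group 2 refers to the single pre-randomisation consent covering both procedures.

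The cost is mainly protocol wording, and following uninjected patients needs no extra visits. With allocation at the visit, both kits and a slot long enough for either procedure must be available each time. The remedy is partial: patients can still refuse at the visit, and those who withdraw consent are lost under any schedule.
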